1 SUMMARY OF CHANGES

Protocol Revision	Protocol Section	Description of Change	Reason for Changes
REV A (October 10, 2017)	N/A	Original issue	Original issue
REV B (December 5, 2017)	Inclusion Criteria: Protocol Summary; Sec. 6.3.1	f. Serum creatinine: 1.5 times ULN changed to “f. Serum creatinine: < 1.5 times ULN”	Editorial Correction: Missing < symbol
	Clinical Events Committee (CEC): Protocol Summary	Removed “in each study arm”	Editorial Correction: Will only have 1 study arm
	Inclusion Criteria: Protocol Summary; Sec. 6.3.1	
2. Biopsy-confirmed BRPC and LAPC in the head or neck of the pancreas that is able to be visualized via CT or other imaging modality (e.g., PET) with no evidence of distant metastasis (AJCC clinical stage IIA-III):
 
 a. Borderline resectable pancreatic carcinoma disease as defined by the NCCN guidelines as follows 
 i. SMV and portal vein: Abutment, encasement, or occlusion of the short segment of vein, ii. Tumor abutment \leq 180 degrees iii. Celiac Axis: Uninvolved celiac axis; short segment encasement or abutment of common hepatic that may be amenable to resection and reconstruction iv. No involvement of lymph nodes b. Locally advanced pancreatic carcinoma disease as defined: 
 i. Major portal vein or superior mesenteric artery (SMA) thrombosis, 	NCCN guidelines clarification based on TIPS investigators' input.

		
ii. Circumferential encasement of the SMA or
 
iii. Involvement of the aorta, celiac axis or proximal hepatic artery.
 
Changed to
 
2. Biopsy-confirmed BRPC or LAPC in the head or neck of the pancreas that is able to be visualized via CT or other imaging modality (e.g., PET) with no evidence of distant metastasis (AJCC clinical stage IIA-III) as defined by the NCCN guidelines:
  
<small>Printed by Augmenix, Inc. on 04/27/17. For personal use only. Not approved for distribution. Copyright © 2017 National Comprehensive Cancer Network, Inc. All Rights Reserved.</small>
	
Post-Injection RT Planning: Protocol Summary; Sec. 6.4.1 Table 2 and Figure 1; Sec. 6.4.8, ICF	5-10 days following Index Procedure changed to “less than 28 days following Index Procedure”	Window can be wider to accommodate patient convenience. RT is typically completed in 5 or 6 fractions and therefore longer duration between TraceIT administration and RT planning/initiation will not impact TraceIT performance (the	

			hydrogel material is stable for 3 months).
	Selection and Training of Investigators: Sec. 6.2	Only radiation oncologists who meet the credentials ... changed to “Only radiation oncologists and physicists who meet the credentials...”	Physicists may be sub-Investigators for this study
	RT Planning: Protocol Summary; Sec 6.4.6; Sec 7.6.3	Changed V33 dose constraint measurement to V35 for proximal duodenum, proximal stomach, small bowel and stomach.	Should match ongoing Alliance trial in same subject population
	Table of Contents	Updated “REFERENCES ERROR! BOOKMARK NOT DEFINED.” to “REFERENCES 47”	Broken link in Table of Contents
Protocol Rev C (March 2019)	Study Title	EARLY FEASIBILITY STUDY FOR EVALUATION OF THE TRACEIT® TISSUE SPACER FOR CREATING SPACE BETWEEN THE DUODENUM AND PANCREAS IN PATIENTS WITH BORDERLINE RESECTABLE OR LOCALLY ADVANCED PANCREATIC CANCER UNDERGOING A COURSE OF SBRT Changed to EARLY FEASIBILITY STUDY FOR EVALUATION OF THE TRACEIT® TISSUE SPACER FOR CREATING SPACE BETWEEN THE DUODENUM AND PANCREAS IN PATIENTS WITH LOCALIZED PANCREATIC CANCER UNDERGOING RADIATION THERAPY	Clarification of resectable pancreatic cancer patient population and radiotherapy.

	Protocol Summary- Study Design	
Multicenter prospective, single-arm early feasibility study. Six (6) subjects with either borderline resectable or locally advanced pancreatic cancer (defined per NCCN guidelines) having completed induction chemotherapy and for whom a course of SBRT is indicated will be enrolled
 
Changed to
 
Multicenter prospective, single-arm early feasibility study. Six (6) subjects with localized (resectable, borderline resectable or locally advanced) pancreatic cancer (defined per NCCN guidelines) having completed induction chemotherapy if required and for whom a course of radiotherapy (RT) is indicated will be enrolled.
	Clarification of resectable pancreatic cancer patient population and radiotherapy.
	Protocol Summary, Protocol	
SBRT (Stereotactic body radiation therapy)
 
Changed to
 
RT (Radiotherapy)
	Clarification of radiotherapy modalities

	
Inclusion Criteria: Protocol Summary; Sec. 6.3.1
	
2. Biopsy-confirmed BRPC and LAPC in the head or neck of the pancreas that is able to be visualized via CT or other imaging modality (e.g., PET) with no evidence of distant metastasis (AJCC clinical stage IIA-III) as defined by the NCCN guidelines:
  
The table defines resectability status based on tumor contact with arterial and venous vessels. It includes categories for Resectable, Borderline Resectable, and Unresectable tumors. Arterial vessels include the Celiac Axis (CA), Superior Mesenteric Artery (SMA), and Common Hepatic Artery (CHA). Venous vessels include the Superior Mesenteric Vein (SMV) and Portal Vein (PV). The table specifies that tumor contact of >180° is generally non-resectable, except for specific anatomical cases like the SMA or CA.
	
Clarification of resectable pancreatic cancer patient population

		
Changed to
 
2. Biopsy-confirmed localized pancreatic cancer in the head or neck of the pancreas that is able to be visualized via CT or other imaging modality (e.g., PET) with no evidence of distant metastasis (AJCC clinical stage IIA-III) as defined by the NCCN guidelines:
	

	
Inclusion Criteria: Protocol Summary; Sec. 6.3.1
	
3.Tumor is clearly delineable from duodenum with at least 1 mm of space visible and no invasion of the duodenum is seen at time of EUS performed for either diagnosis or fiducial placement.
 
Changed to
 
3.Tumor is clearly delineable from duodenum and no invasion of the duodenum is seen at time of EUS performed for either diagnosis or fiducial placement.
 
Inclusion Criteria: Protocol Summary; Sec. 6.3.1
 
5.Radiotherapy or chemoradiotherapy for treatment of the disease is indicated with the intent for eventual surgical resection
 
Changed to
 
5. Radiotherapy or chemoradiotherapy for treatment of the disease is indicated
	
Precise measurements are difficult with current visualization methods and an identifiable delineation is sufficient for enrollment.
 
LAPC by nature cannot always be surgically resected

--	---	--	---

	Exclusion Criteria: Protocol Summary; Sec. 6.3.2	
4. Presence of tumor invasion detected on EUS at time of biopsy
 
Changed to
 
4. Presence of tumor invasion of the duodenum detected on EUS at time of biopsy
	Clarification of location of tumor invasion
	Exclusion Criteria: Protocol Summary; Sec. 6.3.2	
6. Active gastroduodenal ulcer or watery diarrhea
 
Changed to
 
6. Active gastroduodenal ulcer or uncontrolled watery diarrhea
	Clarified to uncontrollable watery diarrhea as many patients are on chemotherapy during screening which can cause watery diarrhea.
	Exclusion Criteria: Protocol Summary; Sec. 6.3.2	
12. Pregnancy, breast-feeding, women of child-bearing age must use contraceptives.
 
Changed to
 
12. Women who are pregnant or breast-feeding; women of child-bearing age must use contraceptives
	Grammatical error
	Screening/Baseline: Protocol Summary	
Subjects who appear to meet the eligibility criteria will be consented for the study and will undergo screening.
 
Information to be collected at this visit includes:
 
Changed to
 
Subjects who appear to meet the eligibility criteria will be consented for the study and will undergo screening.
 
Information to be collected at screening and baseline includes:
	Clarification that the screening/baseline assessments can be done over several days and not at one visit.

	
Protocol Summary: Week 2-6 Following Completion of RT (Restaging & Evaluation for Potential Resection at time of CT)
	
 • CA-19-9 level Pancreaticoduodenectomy should be targeted to be performed 
Changed to
 
 • CA-19-9 level • Pancreaticoduodenectomy should be targeted to be performed 	Typographical error
Section 4		
Adding:
 
A recent study has shown that this outcome may be improved by adding a pre-operative neoadjuvant chemoradiotherapy for resectable patients.⁴ Neoadjuvant therapy has the advantage of reducing the risk of developing metastatic disease in 15 to 35% of patients.⁵
	Justification to include resectable pancreatic cancer patients
Section 4.1.1		Adding: Pre-clinical and clinical investigational studies	Providing new information available for the device
Table 1: TraceIT Tissue Spacer – Component Descriptions		Adding 3mL configuration option	Equivalent material in larger volume, allows for fewer dilution steps
	Section 5	
Six (6) subjects with a biopsy confirmed diagnosis of BRPC or LAPC (AJCC clinical stage IIA-III) having completed a course of induction chemotherapy and indicated for image-guided radiotherapy with SBRT will be recruited...
 
Changed to
 
Six (6) subjects with biopsy confirmed localized pancreatic cancer (AJCC clinical stage IA-III) having completed a course of induction chemotherapy and
	Clarification of radiotherapy modalities; removing reference to stereotactic RT to make protocol more consistent

		indicated for image-guided radiotherapy will be recruited...	
	Section 5	
The study will be conducted at up to 3 investigational sites in the United States. Duration of participation for subjects is approximately 21 months.
 
Changed to
 
The study will be conducted at up to 4 investigational sites in the United States. Duration of participation for subjects is approximately 22 months.
	Opening study to more sites due to lack of enrollment at current sites. Increasing the time for participation to account for longer fractionation schedule
	Section 6.2	
All investigators that will use the investigational device will undergo training per the TraceIT Tissue Spacer Instructions for Use prior to initial use. Additionally, training for injections will be performed via a cadaver lab and/or the use of phantoms.
 
Changed to
 
All investigators that will use the investigational device will undergo training per the TraceIT Tissue Spacer Instructions for Use prior to initial use. Additionally, training for injections will be performed via an animal lab, a cadaver lab and/or the use of phantoms.
	Adding additional appropriate method for Investigator training

	Section 6.4.1	
The schematic of the trial is presented in Table 2, Table 3, and Figure 1.
 
Changed to
 
The schematic of the trial is presented in Table 2, Table 3, and Figure 1.
	Typographical error
	Section 6.4.2	
After the informed consent has been signed, each subject will be entered on a screening/enrollment log, which will be submitted regularly to the Sponsor. Once a subject is consented, a unique 5-digit subject identification number which includes the 2-digit site number plus a sequential 3-digit subject number starting at 001 (e.g., 01-001) will be assigned.
 
Changed to
 
Each subject will be assigned a screening number and will be entered on a screening log, which will be submitted regularly to the Sponsor. After the informed consent has been signed, a unique 5-digit subject identification number which includes the 2-digit site number plus a sequential 3-digit subject number starting at 001 (e.g., 01-001) will be assigned and subject is screened for eligibility criteria and considered enrolled in the study if all eligibility criteria is met.
	Clarification of enrollment definition
	Section 6.4.2	
A subject is considered enrolled in the study at the time of the informed consent.
 
Changed to
	Clarification of enrollment definition

		
A subject is considered enrolled in the study after screening has been completed and the subject meets eligibility criteria.
	
	Section 6.4.5.1	
The subject is to be positioned in the supine position and an endoscopic ultrasound (EUS) will be used to identify the duodenum and HOP interface.
 
Changed to
 
The subject is to be positioned in the left-lateral position and an endoscopic ultrasound (EUS) will be used to identify the duodenum and HOP interface.
	Standard of care for the fiducial procedure is performed in left-lateral position
	Section 6.4.6	
The technique for delivering the external beam treatment will employ stereotactic body radiation therapy (SBRT) techniques using daily image guidance.
 
Changed to
 
The technique for delivering the external beam treatment will be employed per institutional standard guidelines.
	Clarification of radiation therapy
	Section 6.4.14	
6.4.14 Additional Follow-up at Month 3 (\pm 14 days) and Month 6 (\pm 14 days) and Post-Index Procedure
 
Changed to
 
6.4.14 Additional Follow-up at Month 3 (\pm 14 days) and Month 6 (\pm 14 days) Post-Index Procedure
	Typographical error
	Section 6.4.15	
6.4.15 Longer Term Follow-Up
 
Following the 6 month visit, subjects will be followed through to 18 months in accordance with standard of care
	Updated to match study flow figure

	
with at minimum clinical visits performed at Month 12 and Month 18 (\pm 28 days for each visit)
 
Changed to
 
6.4.15 Long Term Follow-Up (Month 12 and Month 18 \pm 28 days for each visit)
 
The following assessments will be performed at the 12- and 18-Month Post-Index Procedure visit:
 
 Physical Examination: including sitting blood pressure, pulse, temperature, weight, anticoagulation status, Zubrod Performance Score. Assessment of duodenal focused Adverse Events documented using NCI CTCAE Other Adverse Events per NCI CTCAE EORTC-QLQ-C30 and QLQ-PAN26 Changes in concomitant medications used to treat intestinal symptoms 		
	
Section 7.4
	
Data may be presented separately for BRPC and LAPC subjects as well as resected and unresected subjects. Details will be provided in the statistical analysis plan
 
Changed to
 
Data may be presented separately for localized (resectable, BRPC and LAPC) subjects as well as resected and unresected subjects. Details will be provided in the statistical analysis plan
	
Inclusion of resectable pancreatic cancer patient population and external beam radiotherapy

	Section 7.5	
The number of subjects signing the informed consent and the number of screening failures (consented but not treated subjects) and the number of secondary screening failures will be presented.
 
Changed to
 
The number of subjects signing the informed consent and the number of primary screening failures (consented but not treated subjects) and the number of secondary screening failures (Duodenal invasion seen at time of index procedure) will be presented.
	Further clarification on primary and secondary screen failures
	Section 7.7	
All adverse events occurring at the time of TraceIT Tissue Spacer injection or attempted injection and up through and including the 6 month visit will be recorded and listed. Thereafter, only information concerning duodenal toxicity or events deemed related to the TraceIT Tissue Spacer will be collected.
 
Changed to
 
All adverse events occurring at the time of initiation of fiducial marker placement or attempted injection and up through and including the 18-month visit will be recorded and listed.
	Further clarification on collection of Adverse Events
	Section 9.1.1	
All Adverse Events (AE) and intervening illnesses must be documented throughout the study.
 
Changed to
 
All Adverse Events (AE) must be documented throughout the study.
	Removing redundancy

	Section 9.1.1	
All adverse events, regardless of severity or relationship to investigational device, will be collected from the time of TraceIT hydrogel injection and through the 18-month visit.
 
Changed to
 
All adverse events, regardless of severity or relationship to investigational device, will be collected from the time of initiation of fiducial marker placement and through the 18-month visit.
	Further clarification of protocol for consistency
	Section 9.1.2	
The CEC will be charged with the following responsibilities:
 
 Continuous review and validation of all adverse events that occur over the course of the study and the subsequent classification of these adverse events as related to the device, or procedure. 
Changed to
 
The CEC will be charged with the following responsibilities:
 
 Continuous review and validation of all adverse events that occur over the course of the study and the subsequent classification of these adverse events as related to the device, procedure, radiotherapy, or other. 	Further clarification of protocol for consistency
	Appendix C: Sample Informed Consent	
You will receive 5 treatments every other day over a period of about 2 weeks.
 
Changed to
	Clarification of radiation therapy

		You will receive radiation therapy as per the institutional standard that will be explained to you by your doctor.	
	Appendix C: Sample Informed Consent	
You will receive radiation treatment for about 2 weeks. During this period, you will receive 5 treatments based on a schedule given to you by your doctor.
 
Changed to
 
You will receive radiation treatment for about 2 – 6 weeks. During this period, you will receive radiation treatments based on a schedule given to you by your doctor.
	Clarification of radiation therapy
	Appendix C: Sample Informed Consent	
About 6 people will be in this study at up to 3 clinics in the United States. You will be in this study approximately 1 year and 9 months beginning with your screening and continuing until your last study visit.
 
Changed to
 
About 6 people will be in this study at up to 4 clinics in the United States. You will be in this study approximately 1 year and 10 months beginning with your screening and continuing until your last study visit.
	Opening study to more sites due to lack of enrollment at current sites. Increasing the time for participation to account for follow-up schedule
	Appendix C: Sample Informed Consent	Adding to Risk section: The risks to an embryo, fetus and breastfeeding baby are not known at this time.	Updating risk section per ICH E6 R2 compliance
	Appendix C: Sample Informed Consent	
Adding: Please indicate below whether you want us to notify your primary care physician or your specialist of your participation in this study.
 
 Yes, I want the study doctor to inform my primary care physician/specialist of my participation in this study.
	Updating consent document per ICH E6 R2 compliance

		
 No, I do not want the study doctor to inform my primary care physician/specialist of my participation in this study.
	
	Appendix C: Sample Informed Consent	
You will be given a copy of this consent document to keep.
 
Changed to
 
You will be given a copy of signed consent document to keep.
	Updating ICF to clarify that subject will be given a copy of the signed consent document
	Appendix D	Investigator Agreement and Certification	Moved from Page 2 to Appendix for ease of use

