	
In accordance with standard medical practice, within 2-6 weeks after completion of therapy, subjects will be restaged to determine whether they may progress to surgery. If surgical resection is attempted and successful, pathological data will be recorded within the study eCRF.
 
All subjects will be evaluated at minimum 3 and 6 months post-TraceIT administration. An MR will be performed at the 6 month visit to evaluate for TraceIT presence. Throughout the duration of the study, subjects will be clinically evaluated and assessed for duodenal adverse events using the grading of the NCI Common Terminology Criteria for Adverse Events (CTCAE v4). Quality of life data will be collected using the EORTC QLQ-PAN26 and QLQ-C30 questionnaires.
 
Additional longer-term follow-up clinic visits will be performed in accordance with standard of care, at minimum, 12 and 18 months.

Safety Endpoints:	
Subjects will be monitored for adverse events and radiotherapy (RT) toxicity (using CTCAE v4) and in particular for the safety endpoint defined as “TraceIT administration procedure-related events which result in a delay in initiation of RT” as reviewed and adjudicated by a Clinical Events Committee.

Effectiveness Endpoints:	
Effectiveness endpoints of interest for this study are as follows:
 
 • Feasibility: Feasibility will be defined to be Technical Success; i.e., the ability to place TraceIT and create space between the duodenum and HOP. • Radiotherapy Benefits: Will be assessed via comparison of pre- and post-TraceIT administration RT plans with consideration of the following: ability to maintain safe duodenal dose constraints, percent/volume of GTV/PTV receiving prescription dose and overall duodenal dose/ dose distribution. 
Additional data collection will include:
 
 • Incidence of resection • Histology of duodenal tissues when resection is performed • Incidence of acute (within 3 months) and late (>3 months) duodenal toxicity (for unresected subjects) • Theoretical dose escalation from post-TraceIT treatment plan • TraceIT persistence (at 6-months post-treatment in nonresected subjects) • Change from baseline in EORTC QoL (QLQ-C30) and QLQ-PAN26 • Comparability of visualization of the fiducial marker and TraceIT hydrogel using a standardized visualization score • Progression free and overall survival through follow-up

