Screening/Baseline: (within 45 days prior to planned TraceIT hydrogel injection)	
Subjects who appear to meet the eligibility criteria will be consented for the study and will undergo screening. Information to be collected at screening and baseline includes:
 
 • Demographic information: date of birth, weight and height, race • Disease documentation: tumor location, initial resectability status, tumor staging, largest pre-treatment dimension of tumor (cm) • Medical/Surgical History/Current status: concomitant medical conditions, prior medical conditions, prior surgeries, prior therapies (e.g., induction chemotherapy) • Physical Examination: including sitting blood pressure, pulse, temperature, weight, anticoagulation status, Zubrod Performance Score • Laboratory testing for hematology plus platelets, creatinine, AST/ALT and bilirubin and baseline serum carbohydrate antigen (CA) 19-9 • Pregnancy test for women of child-bearing potential. • EORTC-QLQ-C30 and QLQ-PAN26 • Assessment of baseline duodenal symptoms per NCI CTCAE • Baseline concomitant medications

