6.4.4 Screening/Baseline Assessments (within 45 days prior to planned TraceIT hydrogel injection)

Subjects who appear to meet the eligibility criteria will be consented for the study and will undergo screening. Information to be collected at this visit includes:

- Demographic information: date of birth, weight and height, race
- Disease documentation: tumor location, initial resectability status, tumor staging, largest pre-treatment dimension of tumor (cm)
- Medical/Surgical History/Current status: concomitant medical conditions, prior medical conditions, prior surgeries, prior therapies (e.g., induction chemotherapy)
- Physical Examination: including sitting blood pressure, pulse, temperature, weight, anticoagulation status, Zubrod Performance Score
- Laboratory testing for hematology plus platelets, creatinine, AST/ALT and bilirubin and baseline serum carbohydrate antigen (CA) 19-9
- Pregnancy test for women of child-bearing potential

- EORTC-QLQ-C30 and QLQ-PAN26
- Assessment of baseline duodenal symptoms per NCI CTCAE
- Baseline concomitant medications

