6.4.9 RT Initiation

RT must be initiated NLT 28 days following TraceIT administration. RT should be initiated NST 1 week from last chemotherapy dose. At the initiation of each fraction, the appearance of the TraceIT hydrogel with respect to presence and material distribution should be compared to RT planning CT.

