9 ADVERSE EVENTS

9.1 Definitions

Adverse Event (AE): Any untoward medical occurrence in a subject that is of new onset or has become worse including consequences of medical therapy resulting from a potential study-related delay in radiation treatment

Adverse events are to be recorded from initiation of fiducial marker placement through the 18 month visit.

Adverse Device Effect (ADE): An adverse event that is believed to have been caused by or is associated with the device.

Serious Adverse Event (SAE): An adverse event that:

- a. Led to death
- b. Resulted in a life-threatening illness or injury
- c. Resulted in a permanent impairment of a body structure or a body function
- d. Resulted in in-patient hospitalization or prolongation of existing hospitalization
- e. Resulted in medical or surgical intervention to prevent permanent impairment to body structure or a body function

The investigator will report serious events to the Sponsor and to his/her IRB per the institution's requirements and as specified in section 8.1.1.

Serious Adverse Device Effect (SADE): A serious adverse event that is believed to have been caused by or is associated with the device.

Unanticipated Adverse Device Effect (UADE): Any serious adverse effect on health or safety, or any life-threatening problem or death caused by, or associated with, a device if that effect, problem or death was not previously identified in nature, severity or degree of incidence in the Investigational Plan, or any other unanticipated serious problem associated with a device that relates to the rights, safety or welfare of subjects.

Event Severity: Event severity will be graded in accordance with the guidelines provided in the NCI Common Terminology Criteria for Adverse Events (CTCAE) v 4.0 (NCI, Oct. 2009). For those events that do not have a term identified in the CTCAE, events should be identified using the following criteria:

Mild: Event causes a low level of inconvenience or discomfort, does not interfere with subject's usual activities, and is usually transient; treatment not ordinarily needed for relief of symptoms.

Moderate: Event causes moderate level of inconvenience or discomfort, may interfere with subject's usual activities; new treatment or change in treatment for symptoms may be needed.

Severe/Serious: Event causes severe discomfort and considerable interference with subject's usual activity and requires treatment and/or hospitalization.

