3.3.1 Statistical Methods

The proportion of resected subjects in the MITT or PP population, localized (resectable, BRPC or LAPC) subgroup may be calculated with an exact (Clopper-Pearson) 95% confidence interval for the true proportion, when appropriate.

The incidence of acute (within 3 months) and late (>3 months) duodenal toxicity for unresected subjects will be reported by CTCAE grade and timing.

Histology of duodenal tissue (Duodenum Damage Score) will be summarized for those subjects when resection is performed.

The summary of theoretical dose escalation from post-TraceIT treatment plan, and , migration and stability at 2-6 weeks post-TraceIT, TraceIT persistence at 6-months post-TraceIT in non-resected subjects will be presented in separated table. The pre-TraceIT and post-TraceIT duodenal space measured by site during index procedure and/or by independent assessors will be summarized separately. Average duodenal space will be

calculated if the measurements were taken from multiple observation points or duplication.

The EORTC QLQ-C30 is a questionnaire developed to assess the quality of life of cancer patients. The pancreatic cancer module QLQ-PAN26 is intended for patients at all disease stages undergoing surgical resection, palliative surgical intervention, endoscopic palliation or palliative chemotherapy. Changes in Quality of Life Measures as assessed overall and subdomains (scales) of the EORTC-QLQ-C30 and QLQ-PAN26 will be evaluated.

The five functional scales (physical, role, emotional, cognitive and social), three symptom scales (fatigue, nausea & vomiting and pain), a global health status/QOL scale, and six single items (dyspnea, insomnia, appetite loss, constipation, diarrhea and financial difficulties) from EORTC-QLQ-C30 will be summarized according EORTC QLQ-C30 Scoring Manual third edition.

The fifteen symptom items and two functional scales from QLQ-PAN26 will be analyzed according EORTC QLQ-PAN26 Scoring Manual 2.2.

Those analysis will be repeated by localized (resectable, BRPC and LAPC), as well as resected and unresected subgroup, if applicable. Scores will be compared to baseline using either a paired t-test or Wilcoxon Signed-Rank test when appropriate.

The result of comparability of visualization of the fiducial marker and TraceIT hydrogel will be summarized using a standardized visualization score for all subjects injected with TraceIT Tissue Spacer.

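### The only quality-of-life baseline is the screening form, up to 45 days before injection and possibly on chemotherapy, so a change in chemotherapy effects can be reported as change after TraceIT and RT

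*Protocol*

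**What the plan says.** **Timing of the baseline.** Protocol Section 6.4.4 is headed "Screening/Baseline Assessments (within 45 days prior to planned TraceIT hydrogel injection", and the Protocol Summary gives the same window. Both place QLQ-C30 and QLQ-PAN26 there. Table 2 (Section 6.4.1) shows neither questionnaire at the index procedure or at post-injection planning. They next appear at the final RT fraction (Section 6.4.10), then at months 3, 6, 12 and 18.

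**Use of the baseline.** The Protocol Summary lists "Change from baseline in EORTC QoL (QLQ-C30) and QLQ-PAN26" among the additional data, and SAP 3.3 makes it an exploratory endpoint. Protocol 7.6.4 calculates change from baseline for all domains. SAP 3.3.1 adds: "Scores will be compared to baseline using either a paired t-test or Wilcoxon Signed-Rank test when appropriate". Neither document says which assessment is the QoL baseline, and neither adjusts for or lists time since chemotherapy.

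**Chemotherapy at screening.** The Rev C entry in Protocol Section 1 that explains the present wording of exclusion criterion 6 says "many patients are on chemotherapy during screening which can cause watery diarrhea". The criterion now excludes only watery diarrhea that is not controlled. The Protocol Summary describes subjects as having finished induction chemotherapy where it was required; Section 5 describes it as finished without that condition. None of the ten inclusion criteria requires it. The one stated interval is in Section 6.4.9: "RT should be initiated NST 1 week from last chemotherapy dose". No rule links chemotherapy to the date of the QoL form.

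**Duodenal symptoms.** Section 6.4.4 includes "Assessment of baseline duodenal symptoms per NCI CTCAE" at screening, and Table 2 schedules the same assessment again at the index procedure.

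**The concern.** There is no control arm, so change from baseline is the only QoL comparison the study can offer, and one form per subject carries it. If some subjects complete that form while on chemotherapy, or shortly after it, and their chemotherapy exposure differs later, the recorded change mixes three things: the injection, the radiotherapy, and the change in chemotherapy effects. The design cannot separate them afterwards.

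The error would be shared. All scales at all follow-up visits use the same baseline, so an offset in it does not average out over visits. Diarrhea, nausea and vomiting, fatigue and appetite loss, which chemotherapy may plausibly affect, are among the QLQ-C30 scales that SAP 3.3.1 names for analysis.

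**Working it through.** **1. Plan's own figure.** The documents give n = 6 with no formula, power or effect size (Protocol 7.1, SAP 3.1.2), so there is nothing to reproduce.

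**2. Longest gaps from the QoL baseline.** Inputs: at most 45 days from screening to planned injection (Protocol 6.4.4); RT no later than 28 days after injection (6.4.9); RT lasting about 2 to 6 weeks (current consent wording, given in the Section 1 Rev C entry).
- To injection: 45 days.
- To RT start: 45 + 28 = 73 days.
- To the final fraction, the first QoL after baseline: 73 + 14 = 87 days to 73 + 42 = 115 days.

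These are upper limits, not typical values. With a form on the index day the first becomes 0 and the second 28 days.

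**3. How much rests on the one form.** QLQ-C30: 5 + 3 + 1 + 6 = 15 scales. QLQ-PAN26: 15 + 2 = 17. Total 32 (SAP 3.3.1). Five follow-up visits give 32 × 5 = 160 comparisons with the same baseline.

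**4. Illustrative size.** The documents give no figures for this step. Assume scales run 0 to 100 with higher meaning better, the SD of change is 20, and k of 6 subjects have a chemotherapy-related shift of d points between screening and injection, of either sign. The shift in mean change is k·d/6, and the standard error is 20/√6 = 8.16.

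| k | d (points) | Shift in mean change | In standard errors |
|---|---|---|---|
| 3 | ±5 | ±2.5 | 0.31 |
| 3 | ±10 | ±5.0 | 0.61 |
| 5 | ±15 | ±12.5 | 1.53 |

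Suppose the true mean change is a worsening of 10 points. By normal approximation, the chance that the observed mean shows no worsening is:
- no shift: P(Z ≥ 10/8.16) = 0.11;
- shift of +5: P(Z ≥ 5/8.16) = 0.27;
- shift of −5: P(Z ≥ 15/8.16) = 0.03.

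**5. Effect on nominal p-values.** Assume no true effect and a pure baseline shift, measured in SDs of the change score. For a two-sided paired t-test with n = 6 (noncentral t), P(p < 0.05) is 5.0% at no shift, 8.0% at 0.25 SD, 17.1% at 0.5 SD, 32.1% at 0.75 SD and 50.7% at 1 SD. The 0.05 level is only a reference here, since the plan sets none. The 95% confidence half-width for a mean change is 1.05 SD, so all but the largest shifts would be hard to see in the data.

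**6. Chemotherapy passages side by side.** Section 1 says many patients are on chemotherapy during screening. Sections 2 and 5 describe induction as complete, with a condition in Section 2 only. Section 6.4.9 fixes an interval before RT and nothing earlier. Read together, they neither establish nor rule out chemotherapy at the time of the QoL form.

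**The case against.** **Induction is described as completed.** Sections 2 and 5 do cut against an on-chemotherapy baseline, and the sponsor's remark says only that chemotherapy can cause diarrhea. This stands against certainty, but the documents do not exclude the problem. The remark may look like superseded log text, but it is the reason for a criterion still in force.

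**Improvement bias.** A reader might infer that the QoL result is biased toward improvement, because follow-up takes place off chemotherapy. The documents do not support that. Inclusion criterion 5 allows chemoradiotherapy, so the form at the final RT fraction may also be on chemotherapy, and nothing bars chemotherapy during follow-up.

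**Duodenal results.** A reader might also infer that recovery from chemotherapy appears as a duodenal change, or that the screening grade is the only reference. Neither holds. Table 2 repeats the assessment at the index procedure. The planned result is the number of subjects with a duodenal event by grade and timing (Protocol 7.7, SAP 3.4.1), not change from baseline. Section 9.1 defines an adverse event as "Any untoward medical occurrence in a subject that is of new onset or has become worse", and Section 9.1.1 sends changes noted before the procedure to medical history. Diarrhea that resolves before injection and returns under RT is therefore of new onset. What remains is that no text says which of the two pre-injection grades is the reference.

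**Low stakes and a partial remedy.** QoL is exploratory, p-values are nominal, and no decision rule uses QoL. A subject could also still be on chemotherapy on the index day. Both points are fair: the first limits the weight of this point, and the second is why a listing is needed as well as a second form. Prior therapies and baseline medications are already collected, which helps to describe exposure but does not give the interval to the form.

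**Conclusion.** The point holds for QoL as a possibility that the design leaves open. The sole pre-treatment form may precede injection by up to 45 days and RT by up to 73, the sponsor says many patients are on chemotherapy at that time, and all 160 planned comparisons use that form without a control arm. Size and sign are unknown. The shifts of 2.5 to 12.5 points (0.3 to 1.5 standard errors) rest wholly on the assumed k, d and SD of 20, and apply equally in either direction.

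With an exploratory endpoint and six subjects, this is an inexpensive improvement to make rather than a threat to the study's main conclusions. For duodenal events, only a minor clarification of the reference grade is left.

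**What to change.** - **Protocol Table 2 and Section 6.4.5:** add QLQ-C30 and QLQ-PAN26 on the index-procedure day, before sedation.
- **SAP 3.3.1:** define QoL baseline as the last assessment before the index procedure, so the screening form serves if the index-day form is missing. List days from last chemotherapy dose to baseline for each subject. The repeat form shortens the gap but does not guarantee a baseline free of chemotherapy effects; the listing shows where that remains.
- **Protocol Sections 1, 2 and 5:** reconcile what is said about chemotherapy at screening with what is said about completed induction.
- **SAP 3.4.1 (minor):** state that the index-day duodenal grade already scheduled in Table 2, taken before the needle is inserted, is the reference for judging a duodenal event as new or worse.

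The cost is one repeat of two questionnaires on a day the subject already attends, one mark in Table 2, a few SAP sentences and one listing. The downside is a small form burden on the procedure day. No treatment changes.
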